## Procedure

In order to recruit the participants, gyms and football clubs across South-Lebanon and Damascus-Syria were visited and information sheets were distributed. These sheets, (1) explained the study purpose, (2) stressed on the voluntary participation and the free will to withdraw from the study, (3) described the experiment process and its duration; (5) stated possible risks and benefits, (6) stressed over confidentiality and (7) provided investigators contact methods.

To start with the experiment, each enrolled participant signed a consent form. Then, an independent examiner who was not involved in the enrollment process had systematically allocated participants into one of the three intervention groups, by withdrawing names randomly out of a bowl. The first draw was assigned to the static stretching group; the second draw assigned to the dynamic stretching group; the third draw assigned to the DTFM group, and so on. In addition, the investigator who entered eligible participants in the study was not aware of which group they were allocated.

The experiment took place in July 2017, over a four weeks period, and participants in each group followed their intervention protocol three times a week, for a total of 12 sessions.

**Static stretching group.** Static stretching was chosen for its effectiveness in increasing both acute and chronic extensibility. All participants laid on the floor in a supine position with both feet pointing upwards. The tested limb was in full knee extension and the foot in a relaxed position and was moved up passively to a point of slight pain or discomfort at the posterior aspect of the thigh. This technique puts the

hamstrings muscle at its greatest possible length. According to the American College of Sports Medicine (ACSM), this position should be held for 30 seconds and was performed three times for a total of one minute and 30 seconds, 15 minutes after a match or training. The contralateral leg was stabilized by means of another collaborator in order to prevent compensation by rotation or elevation of the pelvis.

**Dynamic stretching group.** The dynamic stretching technique was included for its positive effects on agility and muscle strength. Participants in this group, swung their tested leg actively into hip flexion while keeping their knee fully extended and their ankle fully plantar flexed, until a stretch was felt in the posterior thigh. This was repeated over 30 seconds and included in the participant's warm-up phase.

**Deep transverse friction massage group.** Participants were taught by one of the examiners how to sit and perform pre-exercise self-massages on their tested leg MTJ. The procedure consisted of applying friction massage by fingertips transversely to the hamstrings tendon, in a sitting position. The tendon was located over four finger widths proximal to the medial and lateral epicondyles of the femur. One examiner carefully monitored how the technique was performed to assure the precision of the application. This massage technique was applied over a duration of 30 seconds.

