## **Data Collection Methods**

Measurements took place on three occasions, (1) baseline, on the first session; (2) 15 minutes, after the first intervention (acute phase); and (3) after four weeks (chronic phase). In addition, (1) age, (2) height, (3) weight and (4) and injury occurrence rate was recorded for each footballer. On the other hand, flexibility, agility and maximal

voluntary muscle strength measures were taken in the same manner and time for all participants across groups.

[figure not shown]
All measurements were taken by one assessor who didn't know at the time of testing to what group the data belonged to. In addition, this assessor was not involved in the implementation of any of the techniques in this study.

**Flexibility.** Extensibility of the hamstrings muscle represented knee flexibility.

Hamstrings muscle injury is common in sports requiring running. It is usually, the result of a muscle imbalance where the quadriceps muscle is strong and hamstrings are weak and inflexible, what puts a great deal of pressure on the hamstrings leading to injury and strain. Straight leg raise (SLR) is a widely used outcome measure used to assess the extensibility of the hamstrings muscle, where its high reliability makes it an easy and reliable method ICCs of 0.96, and high SEM values (2.2°) and MDD (6°). SLR was first applied to all participants across the groups. All football players laid supine and taught to relax during testing. The tested limb was raised by a volunteer therapist with the knee in full extension and the foot in a relaxed position. The other lower limb was stabilized in a neutral hip rotation and full knee extension by another volunteer. The test was stopped once the therapist felt a strong resistance, or when the pelvic rotation was noted. Then, the assessor placed the goniometer over the greater trochanter, with one arm aligning the lateral femoral condyle, and the other arm aligning parallel to the ground, in a direction to the mid-axillary line and recorded the hip angle. The scores were recorded as degrees of range of movement.

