**Agility.** Agility was chosen to represent the footballer's performance. This athletic event involves elements of speed, change of direction, and varying types of movement. After the measurement of the extensibility, agility was measured by the T-Drill test. The T-Drill has been proven to be a highly reliable testing measurement, ICC (0.95 with 95 % confidence interval). Footballers were instructed on how to perform the T-Drill and on the test procedures. Then, they were instructed to jog for 2 min to warm-up. The participants performed the T-drill twice and the trial with the best time was taken for analysis by the mean of an alert assessor with a stopwatch. Results were measured in seconds and scores were interpreted as (1) excellent, < 9.5; (2) good, 9.5-10.5; (3) average, 10.5-11.5; and (4) poor, > 11.5. A diagram of the T-Drill with its dimensions are shown in (Figure 2).

**FIGURE 2.** Diagram of T-Drill procedure.

**Strength.** Finally, maximal voluntary muscle strength was measured by one repetition maximum (1RM) tests. The ICC for 1-RM test-retest measures was (0.983, 95% confidence interval= 0.964–0.997. After a rest time of 5 min, participants were

guided to the knee flexors strengthening machine (hamstrings curl machine).

Resistance was placed just proximal to the posterior part of the calcaneus bone.

Footballers performed first specific warm-up, consisting of a set of ten repetitions of knee flexion, with a light load. Afterwards, for safety reasons, an estimation of hamstring 1RM was calculated using Brzycki formula [Weight lifted  $\div$  (1.0278 - (0.0278  $\times$  Number of repetitions)]. This formula exhibited a relatively low level of bias (1.6 to 0 kg) and had an ICC above 0.97 and the lower end of the 95% confidence interval was above 0.94.

Maximal voluntary strength was recorded in kilograms.

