## **Data Analysis**

Data were analyzed using the Statistical Package for the Social Sciences (SPSS) version 21.0 for Windows. Descriptive statistics (mean, standard deviation) were calculated to characterize participants' age, weight, and height. Means of the main key variables of the study were also calculated. The Shapiro-Wilk test was used to check the normality of the data distribution. A probability (p) value of  $>0.05$  means that there was no significant difference between groups.

To check for any difference in the incidence of muscle injury between each of the intervention groups, Fisher exact test was used because expected cell count was less than 5.

Dependent t-tests were used to determine any significant differences between the acute and chronic phases of extensibility, agility and muscle strength, and to check the difference between the baseline and chronic phases of these dependent variables.

Analysis of variance (ANOVA) test was used to check for any significant difference between the interventions groups and each of the extensibility, agility, and strength. This test was repeated for three different phases (baseline, acute and chronic). Moreover, after a statistically significant difference was shown between the variables, Tukey's Post Hoc test was used to show where the differences occurred between intervention groups.

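### Players come from two countries, but country is neither in the described draw nor in the between-arm ANOVA, which costs some precision and leaves any chance imbalance unadjusted

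*Combined protocol and SAP*

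**What the plan says.** All references are to the combined protocol and SAP.

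- **Recruitment (Procedure).** "gyms and football clubs across South-Lebanon and Damascus-Syria were visited and information sheets were distributed". The number enrolled from each area is not given.
- **Allocation (Procedure).** An independent examiner allocated players "by withdrawing names randomly out of a bowl", in strict rotation: "The first draw was assigned to the static stretching group; the second draw assigned to the dynamic stretching group", the third to friction massage, and so on. No stratification by country, club or gym is described. The text does not say whether one bowl served both areas.
- **Between-arm analysis (Data Analysis).** "Analysis of variance (ANOVA) test was used to check for any significant difference between the interventions groups" on extensibility, agility and strength. "This test was repeated for three different phases (baseline, acute and chronic"), with Tukey tests after a significant result. No country, site or baseline term is named.
- **Within-player analysis (Data Analysis).** "Dependent t-tests were used to determine any significant differences between the acute and chronic phases", and also for baseline against chronic.
- **Measurement (Data Collection Methods).** "All measurements were taken by one assessor who didn't know at the time of testing to what group the data belonged to". In the straight leg raise (SLR), a volunteer therapist lifted the limb, a second volunteer held the other leg, and the assessor read the angle. For strength, players were "guided to the knee flexors strengthening machine (hamstrings curl machine"), a machine described in the singular. The place of testing is not stated.

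**The concern.** The three outcomes are analysed as raw values: degrees, seconds and kilograms. Players from different countries and clubs may differ on all three before any intervention. If they do, an unstratified draw can by chance give one arm more players from the stronger or more flexible area. The ANOVA as described has no term to remove the resulting shift. Even when the arms happen to be balanced, the between-country variance sits in the residual and widens every between-arm interval.

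The paired t-tests are not exposed in the same way. A stable country difference cancels within a player who is measured under the same conditions each time. It does not cancel in the between-arm ANOVA, which is the only analysis that compares the interventions on these three outcomes.

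**Working it through.** The text gives no sample size, SD, effect size or country split, so there is no stated figure to reproduce. What follows is illustrative.

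**Assumptions, none from the documents:** 10 to 30 players per arm; half of all players from each country; a country difference d of 0.5 or 1.0 within-country SD. The 1:1:1 rotation and the 0.05 threshold come from the plan.

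**1. How uneven can one unstratified draw be?** With n per arm, N = 3n and k players from one country, the chance that the arms receive a, b and c of them is C(n,a)·C(n,b)·C(n,c)/C(N,k). Summing over outcomes where shares differ by at least 20 percentage points gives the first two rows. The SD of the difference in share between two given arms is √[0.25 × (2/n) × N/(N−1)]; for n = 20 this is √(0.25 × 0.1 × 60/59) = 0.16.

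| Per arm | 10 | 12 | 15 | 20 | 30 |
|---|---|---|---|---|---|
| Gap ≥ 20 points, most different pair | 90% | 53% | 65% | 50% | 32% |
| Gap ≥ 20 points, a given pair | 51% | 31% | 37% | 27% | 16% |
| SD of share difference, a given pair | 0.23 | – | 0.18 | 0.16 | 0.13 |

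The rise from 12 to 15 per arm is due to whole-number counts. The shift in an arm contrast is d times the gap in share. A 20-point gap with d = 1.0 shifts it by 1.0 × 0.20 = 0.20 SD; with d = 0.5, by 0.10 SD.

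**2. What does omitting country cost in precision?** With a half-and-half split, the residual variance is 1 + d²/4 in within-country units.

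- d = 0.5: 1.0625, so adjusting multiplies the standard error by √(1/1.0625) = 0.970, about 3% shorter.
- d = 1.0: 1.25, so √(1/1.25) = 0.894, about 11% shorter.

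These ignore the small cost of the lost degree of freedom and of any imbalance itself.

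**3. Type I error and power.** Three-arm ANOVAs were simulated, 5,000 runs per setting, at 10, 15, 20 and 30 per arm. With no true effect, the unadjusted ANOVA after a pooled draw rejected in 4.4% to 5.5% of runs. Power, with one arm better by 1.0 SD and d = 1.0:

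| Per arm | 10 | 15 | 20 | 30 |
|---|---|---|---|---|
| Pooled draw, unadjusted | 49% | 68% | 82% | 95% |
| Pooled draw, country in model | 56% | 77% | 90% | 98% |
| Draw by country, country in model | 58% | 78% | 90% | 98% |

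With d = 0.5, the step from the first row to the third is only 1 to 3 points.

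**4. What is left once baseline is in the model?** Assume a within-country correlation r of 0.7 to 0.9 between baseline and follow-up, and a country difference that is the same at both. Write v = d²/4. Adjusting for baseline alone leaves a fraction (1 − r)/(1 + v) of the country shift.

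- For d = 1.0, the 0.20 SD shift becomes 0.20 × 0.3/1.25 = 0.048 (r = 0.7) or 0.20 × 0.1/1.25 = 0.016 (r = 0.9).
- The residual variance with baseline only is (1 + v) − (r + v)²/(1 + v); with country as well it is 1 − r². For d = 1.0 and r = 0.7 these are 1.25 − 0.9025/1.25 = 0.528 and 0.510, so adding country shortens the standard error by a further 1.7%. For r = 0.9 they are 0.192 and 0.190, a further 0.5%.
- For d = 0.5 the further gain is at most 0.5%.

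**The case against.** Four points can fairly be made on the other side.

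**Differences in equipment and operators.** A reader might infer that each country had its own machine, running surface and testers, and that these differences enter the arm comparison. The documents do not support that. They say where information sheets were handed out, not where players were tested. One assessor, unaware of group, took every measurement, and one curl machine is described. The possibility remains for the SLR, because the volunteer therapist's sense of resistance (or visible pelvic rotation) ended the test, but the text does not say that the volunteers differed by country. This objection stands. The point then rests on players differing between countries, which is plausible but not documented.

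**Bias.** A reader might also infer that the comparison is biased or that false positives rise. Neither follows. Allocation was random, so country is noise on average, and the ANOVA error term already allows for it. This objection stands too.

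**Size.** The 50/50 split and the country difference are assumed, and an uneven split would shrink the problem. The figures for the most different pair look worse than those for any given pair. At 0.5 SD the gain is small, and baseline adjustment would capture most of it. All this is correct, and it limits how much weight the point can bear.

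**One bowl for both areas.** This is the natural reading of the text, not a statement in it. Text before the Procedure section was not available for this review and may give the setting and the numbers per area. Even if the draw was made by country, country still belongs in the model.

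**Conclusion.** The point holds as one of precision. Two recruitment countries are named, no stratified draw is described, and the arms are compared on raw phase values with group as the only named factor. A chance imbalance in country mix is therefore not adjusted for, and any between-country variance stays in the error term.

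Under the assumptions above, omitting country lengthens standard errors modestly. In a small trial with a country difference near 1.0 SD, it could cost roughly 7 to 10 points of power at 10 to 20 players per arm. With a difference near 0.5 SD it costs little. Whether this trial was in fact imbalanced cannot be judged until players per country and arm are reported.

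**What to change.** The Procedure section dates the experiment to July 2017, so the usable change is in the analysis.

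1. In the acute and chronic between-arm models for extensibility, agility and strength, add recruitment country as a fixed factor, alongside the baseline value of the same outcome. Make the pairwise arm comparisons on the adjusted means, with control for the three pairs.
2. Report the number of players per country in each arm, and state whether the draw was pooled, where testing took place, and whether the same machine and SLR volunteers served both areas.
3. If the draw were to be repeated, draw names separately for each country and keep the same three-arm rotation within each.

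The cost is about one degree of freedom per added term. Recruitment area is not among the characteristics listed under Data Collection Methods, so it would have to be taken from the enrolment records.

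### Allocation is described before the first-session baseline, with no statement that players were kept unaware of their arm, so the baseline T-Drill and 1RM are open to performance bias.

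*Combined protocol and SAP*

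**What the plan says.** The Procedure section gives the opening steps in order. First comes consent: "To start with the experiment, each enrolled participant signed a consent form". The next sentence is the allocation: "Then, an independent examiner who was not involved in the enrollment process had systematically allocated participants into one of the three intervention groups", done "by withdrawing names randomly out of a bowl", with successive draws going to the three arms in rotation. No test is described between these two steps. The sessions follow: "participants in each group followed their intervention protocol three times a week, for a total of 12 sessions".

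Data Collection Methods sets the timing of the tests: "Measurements took place on three occasions, (1) baseline, on the first session; (2) 15 minutes, after the first intervention (acute phase"), with a third occasion after four weeks.

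On masking, the same section states: "All measurements were taken by one assessor who didn't know at the time of testing to what group the data belonged to". The Procedure section adds that the investigator who enrolled players did not know their group. Neither section says what the players knew, or when they were told.

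On the tests, the agility subsection says: "The participants performed the T-drill twice and the trial with the best time was taken for analysis". Strength is a maximal voluntary measure on a hamstring curl machine, with 1RM estimated by the Brzycki formula from the load and the number of repetitions. For the straight leg raise, a therapist lifts the limb of a relaxed player and stops at strong resistance or at pelvic rotation.

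**The concern.** Static stretching, leg swings and fingertip self-massage cannot be disguised from the person doing them. If players know their arm when they run the baseline T-Drill and perform the baseline 1RM, their effort may reflect what they expect of that technique. Masking the assessor keeps the recording of the score neutral, but the player still produces the score.

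The baseline value carries particular weight in this plan. The Data Analysis section lists two paired contrasts, acute against chronic and baseline against chronic. The acute measurement is taken after the first intervention, so baseline against chronic is the only planned test of change from a pre-treatment value. If one arm holds back at baseline and tries fully at four weeks, that arm shows an improvement that the technique did not cause. The baseline ANOVA is the plan's check on starting comparability, and it cannot tell an effort difference from a chance imbalance.

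**Working it through.** The plan states no figure on this point, so there is none to reproduce. The check covers the order of events, the tests that depend on effort, and the analyses that use those scores.

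**1. Order.** Procedure: consent, then the draw, then the sessions. Data Collection Methods: "1) baseline, on the first session". Read together, the order is consent, allocation, baseline, first intervention. The description of the straight leg raise speaks of testing players across the groups, which fits groups that already exist at testing.

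**2. Which baseline scores depend on the player's effort.**
- T-Drill: yes. It is the better of two timed runs.
- 1RM: yes. The formula is load ÷ (1.0278 − 0.0278 × repetitions). For a given load, fewer repetitions make the denominator larger and the estimate smaller, so stopping early lowers the score.
- Straight leg raise: not materially. The end point is set by the therapist's sense of resistance or by pelvic rotation.

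**3. Which planned analyses use those scores** (Data Analysis, counted by outcome).
- Paired tests: 3 outcomes × 2 contrasts = 6. Of these, 3 use baseline, and 2 of the 3 rest on an effort-dependent baseline. That is 2 of 6.
- ANOVAs: 3 outcomes × 3 phases = 9. The 6 at the acute and chronic phases use no baseline value. Of the 3 at baseline, 2 concern the T-Drill and 1RM. That is 2 of 9.
- The section does not say whether the paired tests are run within each arm. If they are, the count is 2 × 3 = 6 of 6 × 3 = 18, the same share.

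**4. How an effort shift enters the change.** For one arm, let *b* be the shift in the mean score caused by knowledge of the arm at baseline, and *c* the corresponding shift at four weeks. The observed mean change equals the true mean change plus (*c* − *b*).
- Shift at baseline only (*c* = 0): the bias is −*b*, the whole shift with its sign reversed.
- Stable shift (*c* = *b*): the bias is 0.
- Baseline tested before the arm is known (*b* = 0): the bias is *c*.

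The documents give neither *b* nor *c*, and no SD or sample size, so the bias cannot be evaluated.

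**The case against.** The strongest reply is that allocation is not disclosure. The text says names were drawn. It does not say that players were told before testing, and the order itself is inferred from the sequence of the narrative. Pages and a figure that are not available might bear on it. This stands: players' knowledge at baseline is a possibility left open by silence. It is still a fair point to raise, because no step is described that would have kept the arm from them.

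A second reply is that players also know their arm at the acute and chronic tests. Step 4 shows that a stable effort shift cancels under the described order and does not cancel when baseline is protected. This also stands. Testing before disclosure gives a clean reference, but it does not remove performance bias from these outcomes. No direction can be argued either: all three arms are active, and nothing identifies a favoured one.

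Three stronger readings are tempting, and the documents do not support them.
- *Every change score is affected.* The acute-against-chronic tests do not use baseline, and the straight leg raise is passive.
- *The between-arm comparisons at follow-up are biased through baseline.* The ANOVAs are run separately at each phase, and no comparison of change scores or baseline-adjusted comparison between arms is planned.
- *The bias can be put at a definite size.* With the cited T-Drill ICC of 0.95 and equal variances, the SD of change would be √(2 × 0.05) = 0.316 SD. A shift of 0.1 SD would then be 0.1 ÷ 0.316 = 0.32 of it, or 0.1 ÷ 0.632 = 0.16 if the SD of change were doubled. However, the 0.1 SD is an assumption with no source in the documents, and a cited reliability coefficient is not a four-week correlation across an intervention. These figures show scale only and do not estimate the bias.

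Finally, the text is in the past tense and dates the experiment to July 2017, so reordering may no longer be possible.

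**Conclusion.** The point holds in a limited form. As described, allocation precedes baseline, and nothing says players were unaware of their arm until baseline testing was done. The baseline T-Drill and 1RM are therefore open to performance bias, and so are their baseline-against-chronic paired tests and their baseline ANOVAs: 2 of 6 paired contrasts and 2 of 9 ANOVAs. The rest of the planned analysis is not materially affected by this.

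The conclusion rests on reading the narrative order as the order of events, and on the silence about disclosure being a real gap. It does not show that any player's effort changed. It is worth acting on because the exposed tests are the only planned comparisons of T-Drill and 1RM with a pre-treatment value, and because the remedy is cheap. Confidence is moderate.

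**What to change.** In the Procedure section, put the full baseline battery (straight leg raise, T-Drill, 1RM) after consent and before the bowl draw. If the draw has to come earlier for practical reasons, state that the assignment is withheld from the player until baseline testing is complete.

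If the experiment has already been run, state when players learned their arm relative to the baseline tests. If that was before baseline, qualify the baseline-to-chronic conclusions for T-Drill and 1RM, and note that the baseline ANOVAs for these two outcomes cannot separate effort from chance.

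The cost is small. The order of steps changes, no test is added, and the draw or its disclosure must wait until baseline testing is finished. How much waiting this means is unknown, since the documents do not say how many players were tested per session. The change protects the baseline reference only. Players would still know their arm at the acute and chronic tests, and that limitation should be stated.
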